1.6 Benefit-Risk and Ethical Assessment

The study will be performed in accordance with ethical principles that have their origin in the Declaration of Helsinki and are consistent with International Council for Harmonization (ICH)/Good Clinical Practice (GCP) and applicable regulatory requirements.

MEDI0382 is a GLP-1 receptor and glucagon receptor co-agonist that promotes glucose lowering and weight loss and is targeted at subjects with T2DM. MEDI0382 has the potential to deliver improvements in glycemic control and body weight, and is anticipated to be a useful therapy for T2DM. However, it should be noted that given the short treatment duration in this study little direct benefit to the subject's underlying T2DM should be expected.

Potential risks for MEDI0382 are based on available published data for GLP-1 receptor monoagonists and glucagon receptor monoagonists, as well as clinical and nonclinical data for MEDI0382. Identified risks for MEDI0382 are nausea and vomiting. According to the current IB, potential risks for MEDI0382 include tachycardia, alterations in blood pressure (BP), QT-interval prolongation, anaphylactic-type reactions, injection site reactions, skin rash, pancreatitis, pancreatic carcinoma, and thyroid cancer. The study design aims to minimize potential risks to subjects participating in this study based on the proposed inclusion/exclusion criteria, safety monitoring, and up-titration dosing schedule. Additionally, all subjects will be monitored throughout the study to ensure adequate glycemic control.

Since nausea and vomiting events have been observed in other clinical studies with MEDI0382 and are known class effects associated with marketed GLP-1 receptor agonists, the

study protocol includes strategies to manage GI AEs if they arise. These include reduction of meal sizes, maintaining adequate hydration, and treating the subjects with antiemetics if required. To further mitigate the GI AEs, subjects enrolled in this study will initiate treatment with MEDI0382 at a dose level of [REDACTED] thus introducing two additional titration steps not previously used.

[REDACTED]

[REDACTED]

The investigator will provide a summary of available, relevant, clinical safety data to the medical monitor/sponsor, which will form part of the package of information the Dose Escalation Committee (DEC) will review to make escalation decisions. More information on the DEC can be found in the DEC charter.

Refer to the current IB for further information on the potential benefits of MEDI0382 and an assessment of the potential and known risks.

1.7 Research Hypotheses

1.7.1 Primary Hypothesis

Daily SC administration of ascending doses MEDI0382, titrated weekly to the HCTD will result in an acceptable safety/tolerability profile in overweight/obese subjects with T2DM.

1.7.2 Secondary Hypotheses

- Once daily SC administration of MEDI0382, titrated weekly to the HCTD, will have a predictable pharmacokinetic (PK) and immunogenic profile in overweight/obese subjects with T2DM.

- Once daily SC administration of MEDI0382 titrated weekly to the HCTD, will result in clinically relevant improvement in blood glucose control versus placebo in overweight/obese subjects with T2DM.
- Once daily administration of MEDI0382 titrated weekly to the HCTD, will result in clinically relevant body weight loss versus placebo in overweight/obese subjects with T2DM.

2 OBJECTIVES AND ENDPOINTS

2.1 Primary Objective(s) and Associated Endpoints

Table 1 Primary Objective(s) and Associated Endpoints

Type	Objective	Endpoint
Safety	Assess the safety and tolerability of MEDI0382 titrated up to the highest clinically tolerated dose (HCTD)	
 • Incidence of treatment-emergent adverse events and treatment-emergent serious adverse events through the end of the up-titration period (up to 8 weeks) and through the end of the follow-up period • Clinically important changes in 12-lead electrocardiogram, vital signs (including heart rate and blood pressure), physical examination, and clinical laboratory evaluations through the end of up-titration period (up to 8 weeks) and through the end of the follow-up period

2.1.1 Secondary Objectives and Associated Endpoints

Table 2 Secondary Objective(s) and Associated Endpoints

Type	Objective	Endpoint
PK	To characterize the pharmacokinetic (PK) profile of MEDI0382 titrated up to the highest clinically tolerated dose (HCTD)	
 • AUC over a dosing duration (AUC_{tau}), maximum observed concentration (C_{max}), time to C_{max} (T_{max}), trough plasma concentration (C_{trough}), and accumulation ratio ($C_{min} [R_0]$)
Immunogenicity	To characterize the immunogenicity of MEDI0382 titrated up to the HCTD	
 • Anti-drug antibodies (ADAs) to MEDI0382 at baseline through end of study

Table 2 Secondary Objective(s) and Associated Endpoints

Type	Objective	Endpoint
[REDACTED]	[REDACTED]	[REDACTED]
Efficacy	To assess the effects of MEDI0382, titrated up to the HCTD, on additional measures of glucose control	
 Change in plasma fasting glucose from Day -1 versus each week of the up-titration period, the end of the up-titration period, and the end of the treatment extension period Change in HbA1c from Day -1 to the end of the treatment extension period
Efficacy	To assess the effects of MEDI0382, titrated up to the HCTD, on body weight	
 Percentage and absolute change in body weight from baseline to the end of the up-titration period and the end of the treatment extension Percentage and absolute change in body weight from baseline to the end of each week of the up-titration period

Table 2 Secondary Objective(s) and Associated Endpoints

Type	Objective	Endpoint
		
 Proportion of subjects achieving > 5% body weight loss from baseline to the end of the treatment extension period.

[REDACTED]

[REDACTED]

Type	Objective	Endpoint
[REDACTED]	[REDACTED]	[REDACTED]
[REDACTED]	[REDACTED]	[REDACTED]
[REDACTED]	[REDACTED]	[REDACTED]

3 STUDY DESIGN

3.1 Description of the Study

3.1.1.1 Overview

This is a randomized, blinded, placebo-controlled study designed to evaluate the safety, tolerability, PK and efficacy of ascending doses of MEDI0382 in overweight or obese subjects with T2DM. This study will enroll subjects aged ≥ 18 and ≤ 74 years with a body mass index (BMI) ≥ 27 and ≤ 35 kg/m². Subjects will have a diagnosis of T2DM and inadequate blood glucose control as defined by a hemoglobin A1c (HbA1c) of 6.5% to 8.5%, and will be on metformin monotherapy. Subjects prescribed oral dual therapy with a dipeptidyl peptidase-4 inhibitor, sulphonylurea, glitinide, or a sodium-glucose co-transporter 2 inhibitor in addition to metformin at screening may be eligible to enter the study in Cohort 2 only following a 4-week washout period.

[REDACTED]

[REDACTED]

Subjects will be asked to provide informed consent before undergoing screening assessments to determine their eligibility to participate in the study. Screening will take place within 14 days of subjects starting a 10-day run-in period. The screening period may be extended to up to 42 days for those subjects who are undergoing wash-out from a second anti-hyperglycemic agent. During the run-in period, subjects will refrain from taking prohibited medications but will continue to take their prescribed stable dose of metformin as they will for the duration of their participation in the study.

, and may receive further training in self injection technique if required, as determined at the screening visit. An ambulatory blood pressure monitoring (ABPM) device will be fitted and worn for 24 hours.

Following the run-in period, subjects will be admitted to the clinical unit on Day -2 and will undergo initial safety assessments and blood tests. At this time, an ABPM device will be fitted and worn for 24 hours;  Subjects will be expected to wear a sensor continuously until the end of the study, which will require periodic replacement. Following an overnight fast, subjects will be weighed on the morning of Day -1, and further blood tests and a series of electrocardiograms (ECGs) will be conducted. Subjects will eat a standardized, breakfast, lunch, and evening meal at given times without consuming any other food until the following day. Eligibility criteria will also be reverified prior to dosing. Subjects will be randomized at any time from Day -1 to prior to receiving a MEDI0382 or placebo dose on Day 1.

[figure not shown]

[REDACTED]

[REDACTED]

After the initial titration period to determine the HCTD, subjects will continue at the HCTD for a further 3 weeks, returning to the clinical unit at Day 7 (for an outpatient visit) and Days 20-21 (for an inpatient visit) of the treatment extension for safety and efficacy assessments and resupply of investigational product as required. A follow-up visit will be performed for final safety assessments 28 days after the last dose of investigational product or as convenient in the event of discontinuation.

Subjects in Cohort 2 will follow the up-titration schedule defined by Cohort 1, with the 3-week treatment extension period being conducted at the HCTD; thus, the duration of Cohort 2 subjects' participation in the study will be determined by the results obtained from Cohort 1. Dosing in Cohort 2 will occur ≥ 7 days after initiation of Cohort 1.

3.1.2 Treatment Regimen

Following randomization, eligible subjects will receive either MEDI0382 or placebo (3:1 ratio) once daily in the morning via SC injection.

MEDI0382 will be administered for up to 8 weeks during the up-titration period to determine the HCTD as follows:

A table with two columns. The first column contains a vertical list of eight small blue rectangular redaction marks. The second column contains a vertical list of eight larger blue rectangular redaction marks, each corresponding to a row in the first column. The text within these redactions is completely obscured.

[REDACTED]

[REDACTED]

[REDACTED]

3.1.3 Dose Escalation

[REDACTED]

If progression to the next dose level is not endorsed by the DEC, the prior dose level will be declared as the HCTD. Subjects will be down titrated to the HCTD on the next feasible dosing day and complete the 7-day dosing period at that level. The 3-week treatment extension will be triggered from the end of that 7-day dosing period.

More detailed information on dose escalation can be found in the DEC charter.

3.1.3.1 Dose Escalation Committee

A DEC will be formed for safety data review and monitoring. The DEC will also make decisions on progression to treatment at a higher dose or on meeting dose escalation stopping criteria as outlined in the DEC Charter.

Relevant available safety data will be reviewed at the DEC meeting for subjects at the current dose period as well as the cumulative safety data (including data that are not yet source document verified such as laboratory values, AEs, ECG, and vital signs) to date, to make an informed decision on whether to dose escalate or not.

After reviewing the data from a given dose period, the DEC will make one of the following decisions:

- Escalate to the next dose level
- Stop dose escalation and proceed to 3-week treatment extension at the HCTD.

- Request for review and decision by the MedImmune Safety Review Board on how to proceed, or whether to suspend or stop the study.

The rules for dose escalation are discussed in Section 3.1.3.2.

3.1.3.2 Dose Escalation Stopping Criteria

Dose escalation will be stopped if the DEC determines that any of the following criteria are met.

- More than 50% of subjects treated with MEDI0382 in a specific dose period experience grade 2 or higher AEs assessed as related to MEDI0382 and require discontinuation of MEDI0382
- One serious adverse event (SAE) occurs in a MEDI0382 subject that is assessed as related to MEDI0382
- Two or more subjects receiving MEDI0382 experiences any of the following:
 - An average absolute (regardless of baseline value) cardiac QTc interval corrected for heart rate by the formula of Fridericia (QTcF) > 500 msec, or an increase of QTcF > 60 msec above the baseline value, confirmed (persistent for ≥ 5 minutes) on a repeat 12-lead ECG
 - Tachycardia, defined as resting supine heart rate > 125 beats per minute persisting for at least 10 minutes (measured at 5 timepoints in the 10-minute period)
 - Symptomatic bradycardia, defined as resting supine heart rate < 40 beats per minute while awake, persisting for at least 10 minutes; or asymptomatic bradycardia defined as resting supine heart rate < 30 beats per minute while awake persisting for at least 10 minutes (measured at 5 timepoints in the 10-minute period)
 - Hypertension, defined as an increase from baseline in resting supine systolic blood pressure (BP) > 40 mmHg or above 180 mmHg and persisting for at least 10 minutes, or an increase from baseline in resting supine diastolic BP > 20 mmHg or above 100 mmHg and persisting for at least 10 minutes
- The above cardiac criteria do not apply if provoked by complicated venepuncture or other vagal provocation

If any of these criteria are met, then the DEC will either:

- Recommend that the study proceed to 3-week treatment extension at the HCTD, or
- Request for review and decision by the MedImmune Safety Review Board on how to proceed or whether to suspend or stop the study

3.1.4 Management of Study Medication Related Toxicities

GI Tolerability

In this study, dose escalation may be limited by GI tolerability, specifically with respect to nausea and vomiting

Prior to receiving investigational product, subjects will be advised that transient nausea and vomiting are possible and will receive counseling about meal size and eating habits. Specifically, subjects will be advised to avoid administering the medication close to a large or high-fat meal; to consume small, frequent meals 4 to 5 times a day that are low in fat and insoluble fibers; and to stop eating when they are feeling full. Subjects will also be advised to avoid carbonated beverages, alcohol, and smoking to help prevent the occurrence of nausea and vomiting. This advice should be reiterated should symptoms of nausea and vomiting occur once investigational product dosing has initiated. If symptoms do not improve despite a change of dietary habits, metformin may be withheld for 3 days, or alternatively, subjects should be offered antiemetic therapy in accordance with institutional and local practice guidelines. A centrally acting antiemetic such as a 5HT-3 antagonist (eg, ondansetron) or cyclizine is the preferred treatment in the first instance, rather than a prokinetic agent such as domperidone or metoclopramide.

Hyperglycemia

In the unlikely event of suspected persistent hyperglycemia in a subject based on either symptoms of hyperglycemia (eg, thirst, polyuria, blurred vision), capillary blood glucose readings (eg, 3 readings > 260 mg/dL [14.4 mmol/L] within one week), the investigator should perform additional fasting blood glucose levels as necessary to further investigate, and subjects should be asked to monitor capillary plasma glucose levels up to 5 times per day. If 2 or more laboratory plasma fasting glucose levels of > 260 mg/dL [14.4 mmol/L] taken at least 3 days apart are detected, the subject should be discontinued from the study (Section 4.1.6), and rescue therapy should be considered in line with current local guidelines.

Hypoglycemia

Any blood glucose level 54 mg/dL (< 3.0 mmol/L) with or without symptoms is considered as clinically significant hypoglycemia and should be reported by the Investigator as an AE. Spontaneous and clinically significant hypoglycemia has not been observed in prior studies with MEDI0382 up to a dose of 300 µg alongside metformin treatment. All subjects will be provided with a glucometer and will be advised to check their capillary blood glucose level if they have symptoms of hypoglycemia (hunger, dizziness, shaking, sweating, or irritability) or feel unwell. Any such subjects should be managed using local protocols for treatment and follow-up of any hypoglycemic episode. Pharmacological treatments administered for hypoglycemia, eg, dextrose/glucose tablets, glucose infusion, glucagon injection etc, should be recorded in the electronic case report form (eCRF) as concomitant medications.

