4.1.5 Withdrawal from the Study

Subjects are free to withdraw their consent to participate in the study (investigational product and protocol-defined assessments) at any time, without prejudice to further treatment. Subjects who withdraw consent will be asked about the reason(s) and the presence of any AEs. If the

subject is willing, the subject will be seen and assessed by the investigator (early discontinuation visit). AEs will be followed up, and all study medications should be returned by the subject. If a subject withdraws from further participation in the study, then no further study visits or data collection should take place.

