4.1.6 Discontinuation of Investigational Product

An **individual subject** will not receive any further investigational product if any of the following occur in the subject in question:

- 1 Withdrawal of consent from further treatment with investigational product
- 2 Lost to follow-up
- 3 An AE that, in the opinion of the investigator or the sponsor, warrants discontinuation of further dosing
- 4 Pregnancy in a female subject (see Section 5.6.2 for additional details regarding pregnancy)
- 5 Signs or symptoms of severe hepatic impairment including abnormal laboratory values according to below:
 - (a) ALT and/or AST are $> 3 \times \text{ULN}$ and TBL $> 2 \times \text{ULN}$
 - (b) ALT and/or AST are $> 5 \times \text{ULN}$ for ≥ 14 consecutive days, at any time after initial confirmatory results
 - (c) ALT and/or AST are $> 8 \times \text{ULN}$
- 6 Average absolute (regardless of baseline value) cardiac QTc interval corrected for heart rate by QTcF > 500 msec, or an increase of QTcF > 60 msec above the baseline value, confirmed (persistent for ≥ 5 minutes) on a repeat 12-lead ECG
- 7 Any one of the following:
 - (a) **Tachycardia**, defined as resting supine pulse rate > 125 beats per minute persisting for at least 10 minutes
 - (b) **Symptomatic bradycardia**, defined as resting supine pulse rate < 40 beats per minute while awake, persisting for at least 10 minutes
 - (c) **Asymptomatic bradycardia**, defined as resting supine pulse rate < 30 beats per minute while awake persisting for at least 10 minutes
 - (d) **Hypertension**, defined as an increase from baseline in resting supine systolic > 40 mmHg or above 180 mmHg and persisting for at least 10 minutes and/or increase from baseline in resting supine diastolic BP > 20 mmHg or above 100 mmHg and persisting for at least 10 minutes
- 8 Persistent hyperglycemia detected as 2 or more laboratory plasma fasting glucose levels of > 260 mg/dL (14.4 mmol/L) taken at least 3 days apart are detected

Subjects who are permanently discontinued from receiving investigational product will be followed for protocol-specified assessments including the 28-day post-last-dose safety follow-up visit and continued follow-up of any AEs unless consent is withdrawn from further study participation, the subject is lost to follow-up, the subject starts alternative treatment, or the subject is enrolled in another clinical study.

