4.7.2 Prohibited Concomitant Medications

Other than the medications described above, use of the following medications, including over the counter medications, herbal supplements, vitamins etc. at the times specified in the list below is not permitted, generally speaking from the time specified in the entry criteria until after the 28-day post-last-dose safety follow-up visit

Subjects should not be initiated on any new medications to control blood glucose levels during the dosing and follow up period unless it is deemed necessary by the Investigator for safety and following discussion with the Medical Monitor.

- Concurrent or previous use of a GLP-1 analogue containing preparation within the last 30 days or 5 half-lives of the drug, whichever is longest, prior to the start of screening (Visit 1)
- Concurrent or prior use of any herbal preparations or dietary supplements marketed for control of body weight or appetite within 1 week prior to the start of screening

- Concurrent or previous use of drugs approved for weight loss (eg, orlistat, bupropion-naltrexone, phentermine-topiramate, phentermine, lorcaserin) within the last 30 days or 5 half-lives of the drug, whichever is longest, prior to the start of screening
- Antidepressant (eg, escitalopram) or anti-psychotic agents (eg, chlorpromazine) must not be started during the course of the study.
- Systemic corticosteroids by oral, intravenous, intra-articular, or intramuscular route are prohibited within 3 months prior to screening and during the study unless prescribed for a very brief period of less than 7 days.
- Concurrent use of aspirin (acetylsalicylic acid) at a dose greater than 150 mg once daily and within the last 72 hours prior to the start of the study (Visit 2)
- Concurrent use of paracetamol (acetaminophen) at a total daily dose greater than 3000 mg once daily and within the last 72 hours prior to the start of the study (Visit 2)
- Concurrent use of ascorbic acid (vitamin C) at a total daily dose of > 1000 mg and within the last 72 hours prior to the start of the study (Visit 2)
- Concurrent use of medications (other than metformin) for control of blood glucose within 4 weeks prior to the start of the study (Visit 2) unless it is deemed necessary by the investigator for safety reasons.
- Antimicrobials within the quinolone (eg, ciprofloxacin), macrolide (eg, clarithromycin) or azole class (eg, ketoconazole)

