6.3 Study Timetable and End of Study

An individual subject will be considered to have completed the study if the subject was followed through their last protocol-specified visit/assessment (including telephone contact) regardless of the number of doses of investigational product that was received.

Subjects will be considered not to have completed the study if consent was withdrawn or the subject was lost to follow-up (see Sections [4.1.5](#) and [4.1.6](#)).

The end of the study (“study completion”) is defined as the date of the last protocol-specified visit/assessment (including telephone contact) for the last subject in the study.

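### For the same persistent-hyperglycemia trigger, Protocol 3.1.4 removes the subject from the study while 4.1.6 stops only product, and 4.1.6 can be read as ending follow-up once rescue starts

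*Protocol*

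**What the plan says.** Protocol 3.1.4, under hyperglycemia, sets a laboratory trigger and then directs that "the subject should be discontinued from the study (Section 4.1.6), and rescue therapy should be considered in line with current local guidelines".

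Protocol 4.1.6, whose title concerns stopping investigational product, lists as item 8 "Persistent hyperglycemia detected as 2 or more laboratory plasma fasting glucose levels of > 260 mg/dL (14.4 mmol/L) taken at least 3 days apart". Its lead-in says only that such a subject receives no more product. It then adds: "Subjects who are permanently discontinued from receiving investigational product will be followed for protocol-specified assessments". That sentence names the 28-day safety visit and continued follow-up of adverse events. It has four exceptions: withdrawn consent, loss to follow-up, enrolment in another trial, and the case where "the subject starts alternative treatment".

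Three other sections bear on the point:

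- Protocol 4.1.5, written for subjects who withdraw consent: "If a subject withdraws from further participation in the study, then no further study visits or data collection should take place".
- Protocol 4.7.2 bars starting "new medications to control blood glucose levels during the dosing and follow up period unless it is deemed necessary by the Investigator for safety", after discussion with the medical monitor.
- Protocol 6.3 counts a subject followed to the last specified visit as a completer "regardless of the number of doses of investigational product that was received". It names only consent withdrawal and loss to follow-up as non-completion.

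The primary endpoint in Protocol 2.1, Table 1, covers adverse events "through the end of the up-titration period (up to 8 weeks) and through the end of the follow-up period".

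**The concern.** The protocol treats leaving the study and stopping product as separate events with separate consequences, so the noun in 3.1.4 matters in practice. A site that acts on 3.1.4 as printed could close the subject out.

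A site that follows the cross-reference meets a second difficulty. The sentence in 3.1.4 that stops treatment also advises rescue therapy, and 4.1.6 releases a subject from follow-up once other treatment begins. For this trigger, the exception can cancel the rule it qualifies.

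At stake is the adverse-event and safety follow-up of a rescued subject between the last dose and the 28-day visit. That interval belongs to the primary endpoint, and Protocol 5.4.1 collects all adverse events through it.

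**Working it through.** The plan gives no figure to reproduce; the check is mainly a comparison of texts.

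**1. Trigger.** Protocol 3.1.4 and 4.1.6 item 8 agree on every element: at least 2 laboratory fasting plasma values, above 260 mg/dL (14.4 mmol/L), at least 3 days apart. The sections therefore govern the same subjects.

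**2. Action.** 3.1.4: out of the study, with rescue considered. 4.1.6: off product, with assessments continuing. Taken literally, these cannot both be followed.

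**3. Likelier intent.** Three texts favor stopping product only. 3.1.4 itself points to 4.1.6. Section 6.3 does not list removal by the investigator as non-completion. Section 4.7.2 contemplates new glucose-lowering drugs being started for safety while dosing or follow-up is still under way.

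**4. The exception.** Accept that reading and apply 4.1.6 to a rescued subject. Its exceptions qualify both the 28-day visit and the adverse-event follow-up. Whether rescue counts as alternative treatment is not stated in any visible text. Section 4.7.2 permits the drug but does not say that assessments go on. Correcting 3.1.4 alone therefore leaves the gap open.

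**5. Timing of the last visit.** Section 3.1.1.1 and the synopsis place the follow-up visit 28 days after the last dose, but after a discontinuation they let it be held whenever convenient. Nothing there protects the 28-day interval.

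**6. Size for one subject.** Let d be the number of days from last dose to last contact.

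- Follow-up lost = 28 − d days.
- If the last contact is on the stopping day, d = 0 and the loss is 28 − 0 = 28 days.
- Table 7 allows ±3 days on the visit, so the full interval is 28 − 3 = 25 to 28 + 3 = 31 days.

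**7. Share of an arm, for scale only.** Randomization 3:1 in cohorts of 8 and 12 gives 6 + 9 = 15 on MEDI0382 and 2 + 3 = 5 on placebo. One subject is 1/15 = 6.7% or 1/5 = 20% of an arm. This is not an effect on the endpoint: the subject stays in the As-treated population (SAP 3.2), and events already recorded still count.

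**The case against.** The strongest reply is that this is an editorial slip the protocol already resolves. The sentence in 3.1.4 cites the section with the right rule, and the ban on further data collection in 4.1.5 is written for consent withdrawal, not for a decision by the investigator. The protocol also uses separate words for rescue (3.1.4, 5.6.3) and for alternative treatment (4.1.6), which suggests they differ. Much of this stands, and it is why the point is minor. It does not dispose of the exception in 4.1.6, because a difference in vocabulary is not a definition and no visible text says that rescue leaves follow-up intact.

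There are also partial safeguards. The last column of Table 7 serves as both the 28-day and the early discontinuation visit, so a subject seen early would still have vital signs, ECG, weight and blood tests. Section 5.4.2 has the investigator follow unresolved events as long as medically indicated. But an early visit cannot capture events that start later, and follow-up under 5.4.2 is not recorded in the eCRF.

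A reader might infer that the treatment-extension assessments in Table 7 would be lost as well. The documents do not support counting them. The extension is defined as treatment at the HCTD, and nothing visible says that a subject off product attends it. With a full 8-week titration, extension Day 7 is study Day 56 + 7 = 63 and extension Day 21 is Day 56 + 21 = 77. A last dose before Day 63 − 28 = 35 puts the subject's own 28-day visit before the first of these, and a last dose before Day 77 − 28 = 49 puts it before the second. For many stops during titration, those assessments would fall after the final visit even under perfect wording.

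**Conclusion.** The conflict between 3.1.4 and 4.1.6 is real, and the exception in 4.1.6 makes it more than a wrong noun. The consequence is limited: a rescued subject could lose up to about 28 days of safety follow-up after the last dose. This assumes that a site reads 3.1.4 literally, or treats rescue as alternative treatment, and makes its last contact on the stopping day. The protocol calls the event unlikely and gives no rate. Severity is minor.

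Two stronger readings go beyond the documents:

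- A reader might infer a bias, perhaps falling on the five placebo subjects. In Cohort 2, washed-out subjects may enter with fasting glucose up to just under 225 mg/dL, 260 − 225 = 35 mg/dL below the trigger, and those on placebo then have metformin alone. That makes the event conceivable, but without a rate by arm no size or direction can be stated.
- A reader might infer that the SAP has no rule for values taken after rescue. The text after the last-observation-carried-forward sentence in SAP 3.4.2.2 is redacted, so such a gap cannot be shown. Table 6 is not visible either, so what would be missed during titration is unknown.

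**What to change.** Three wording changes to the protocol:

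1. In 3.1.4, have the trigger discontinue the subject from investigational product instead of from the study, keeping the reference to 4.1.6.
2. In 4.1.6, state that starting glucose rescue therapy is not alternative treatment that ends follow-up, so that adverse-event collection and the safety visit 28 days after the last dose continue.
3. In 3.1.1.1 and the synopsis, limit the allowance for a conveniently timed follow-up visit to subjects who withdraw consent or will not return at 28 days.

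The cost is a small wording amendment. The 28-day visit is already scheduled, and no sample size changes. The downside is that some safety data would be collected under rescue therapy and must be read with that in mind. No SAP change is required by this point.
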